Statistical Analysis Plan

December 21st, 2023

NCT01817166

PHRC-N/2012/ET-01

Efficacy of Cholecalciferol (Vitamin D3) for Delaying the Diagnosis of MS After a Clinically Isolated Syndrome

Final detailed statistical analysis plan drafted before data lock and before the commencement of statistical analyses.

An initial data analysis will provide a description of each arm. Statistical results will be presented using mean and standard deviation for quantitative variables with a Gaussian distribution, and median and interquartile range for other quantitative variables. For qualitative variables, frequencies and associated percentages will be presented.

Demographic, clinical (initial relapse), radiological (diagnostic MRI), and biological (lumbar puncture, vitamin D) data will be described. In particular, it will be determined for each patient whether the diagnostic criteria of McDonald 2017 are met at inclusion (Thompson et al., 2018).

The statistical analysis will be conducted by the BESPIM of the CHU de Nîmes using R 4.1.1 or a later version (R Core Team (2021). R Foundation for Statistical Computing, Vienna, Austria).

Primary Analysis (Rate of EDA)

The primary objective is to assess the efficacy and tolerance over 2 years of treatment with Cholecalciferol (Vitamin D3) in patients who have experienced a clinically isolated syndrome at high risk of multiple sclerosis (CIS, according to the McDonald criteria of 2005). This efficacy will be measured by comparing the risk of conversion to relapsing-remitting multiple sclerosis (RRMS) within 2 years after CIS, according to 2005 McDonald criteria (new lesions on follow-up brain and spinal cord MRIs or new relapses) (McDonald et al., 2001; Polman et al., 2005), between the arm receiving Cholecalciferol and the arm receiving the placebo.

Following the actual diagnostic criteria for MS (McDonald 2017), most patients present with a diagnosis of active MS and conversion corresponds to the current concept of EDA (evidence of disease activity defined by clinical relapses or imaging (gadolinium-enhancing lesions or new or unequivocally enlarging T2/FLAIR lesions) (Lublin et al., 2013) an "no conversion" corresponds to NEDA (no evidence of disease activity). Hence, the event will be the occurrence of EDA within the two years of follow-up (relapse and/or appearance of new or enlarging lesions (NEL) on follow-up MRIs at 3, 12, and 24 months).

Patients lost to follow-up before experiencing EDA will be considered as not having had the event. A sensitivity analysis with the maximum bias assumption will be conducted by considering missing data (discontinuation of follow-up before the end of the 2-year follow-up with NEDA) in the interventional arm as failures (non-responders = EDA) and those in the control arm as successes (responders = NEDA).

The rate of EDA in both arms will be estimated and then compared between the two treatment arms using mixed-effects logistic regression (random center effect). The treatment arm will be the factor of interest in the model. Adjustment will be made for randomization stratification factors (center, contrast enhancement on diagnostic brain and spinal cord MRI), known prognostic factors listed in section 4.1.4 of the protocol (Age, Gender, Presence of contrast enhancement on the reference MRI, Lesion load in FLAIR in mm³, Number of lesions with contrast enhancement on the reference MRI, EDSS score at baseline), and the time between CIS and the first administration of the treatment, which varies among patients (from a few days to 95 days = maximum of 90 days between CIS and the reference MRI and the first administration of the study treatment, which takes place on the first Saturday post-MRI). Adjustment for the center effect will be performed by considering the center as a random effect in the model (Kahan 2014, Kahan et al. 2015, Edgar et al. 2021).

The number of lesions with contrast enhancement on the reference MRI could not be determined quantitatively. This information is provided by recording the presence of contrast enhancement with a precision level in 3 modalities (similar to the diagnostic MRI): no lesions with contrast enhancement, one lesion with contrast enhancement, and at least two lesions with contrast enhancement. This information will be used as an adjusting variable only if it is not significantly associated with contrast enhancement on the diagnostic MRI (a randomization stratification factor), for which an adjustment is performed. The statistical significance of the association will be assessed using the Chi-square test or Fisher's exact test if the Chi-square test is not applicable, with a significance level set at < 0.05.

Furthermore, the lesion load in FLAIR in mm³ (reference MRI) is available only for 258 out of 316 patients (those for whom the MRI images could be retrieved). Moreover, obtaining this volume is not reliable because the software does not provide a sufficiently precise estimate. Therefore, no adjustment will be made for the lesion load, and the number of T2/FLAIR lesions on the reference MRI will be used instead as an indicator of lesion load (in 2 modalities: <9 lesions, >= 9 lesions).

In the event of the use of an incorrect stratum during randomization (randomization performed for the stratum with contrast enhancement on the diagnostic MRI while the true value was an absence of contrast enhancement, and vice versa), the analyses will be adjusted for the contrast enhancement value on the diagnostic MRI (Yelland et al., 2022). The stratum error rate will be described by arm.

Primary Analysis (Time to EDA)

Time to EDA is the duration between the date of the first administration of the experimental treatment and the date of EDA.

Date of EDA is:

- The date of the "conversion MRI" for patients with EDA determined by the appearance of NEL on MRI without having a relapse during the follow-up,

- The date of the first symptoms of a relapse for patients with EDA determined by a new relapse without the appearance of NEL on MRI during the follow-up,

- The earlier of the two dates between the date of the first symptoms and the date of the MRI showing NEL for patients who have both a relapse and NEL on MRI during the follow-up.

Patients lost to follow-up or not showing EDA during the follow-up will be right-censored at the date of the last news. The endpoint date will be established for each patient at the date of the end-of-study visit conducted 24 months (2 years) after inclusion.

Time to EDA in both arms will be graphically represented using the Kaplan-Meier method.

The proportional risk of EDA in the experimental arm compared to the placebo arm will be estimated along with its 95% confidence interval using a random-effects Cox model (random center effect) after checking the proportional hazards assumption. Adjustment will be made for the same variables as those used when analyzing the rate of EDA.

Secondary Analyses

Secondary Objective A: Evaluate clinical efficacy on the number of relapses during the study period. The determination of the number of relapses is based on data from the EDA visit and the summary table of relapses based on the evaluation at Month 24. The number of relapses will be compared between the two arms using a non-parametric Mann-Whitney Wilcoxon test.

Secondary Objective B1: Describe the parameters of magnetic resonance imaging (brain and spinal cord MRI) at the "conversion MRI":

- Appearance of NEL on brain MRI in T2/FLAIR (including size increase) and/or on spinal cord MRI in T2 ("conversion MRI" Yes/No)

- New brain or spinal cord gadolinium-enhancing T1 lesions (active lesion(s) Yes/No)

- Lesion load in mm³ of each brain MRI from the FLAIR sequence

- Total number of gadolinium-enhancing T1 lesions (categorical measure: none, one, at least two)

Secondary Objective B2: Describe the magnetic resonance imaging (brain and spinal cord MRI) parameters during follow-up:

Normalized brain volume obtained from the 3D T1 sequence at different visits
Change in global brain volume (mm3, from the 3D T1 sequence) between the baseline examination and the 2-year examination on one hand, and between the 3-month examination and the 2-year examination on the other hand, to limit the effect of pseudo-atrophy after the first relapse

Secondary Objective C: Evaluate efficacy on disability progression, measured by the EDSS score and Kurtzke functional scores (Kurtzke 1983; Noseworthy et al. 1990; Goodkin et al. 1992) at baseline and during follow-up, then considering scores at M0 and M24 only.

Secondary Objective D: Evaluate efficacy on cognitive abilities (PASAT) (Cutter et al. 1999; Fischer et al. 1999; Parmenter et al. 2006) at baseline and during follow-up, then considering scores at M0 and M24 only.

Secondary Objective E: Evaluate efficacy on quality of life (EQ5D, SF36, TLS-QoL10, and TLS-COPING10 questionnaires), fatigue (FSMC questionnaire), and anxiety/depression (HADS questionnaire) at baseline and during follow-up, then considering scores at M0 and M24 only.

For Objectives C, D, and E:

- A first mixed-effects regression model will be used to compare the evolution of the outcome measures (EDSS score for Objective C, PASAT score for Objective D, and quality of life scores for Objective E). The model variables will include:
 - Scores at different visits (outcome variables)
 - Treatment arm (explanatory variable of interest)
 - Center as a random effect (multiple patients per center)
 - Patient as a random effect (multiple measurements per patient)
 - Visit (temporal chronological variable)
 - Interaction between the treatment arm and the presence of a relapse during follow-

up

- A second mixed-effects regression model will be used to compare the M24 scores of the outcome measures while adjusting for baseline scores (M0):
 - M24 score (outcome variables)
 - Treatment arm (explanatory variable of interest)
 - Center as a random effect (multiple patients per center)
 - M0 score (adjustment variable)

- Interaction between the treatment arm and the presence of a relapse during follow-up

Secondary Objective F: Evaluate treatment tolerance on:

a. The occurrence of AEs and SAEs

- b. Pharmacological measurement of serum concentrations of 25(OH)D2 and 25(OH)D3
- c. Measurement of serum calcium, urinary calcium, and renal function

The number of AEs and SAEs per patient will be described by arm.

For points b and c, a mixed-effects regression model will be used to compare the evolution of measurements during follow-up. The model variables will include:

- Measurements at different visits (outcome variable)
- Treatment arm (explanatory variable of interest)
- Center as a random effect (multiple patients per center)
- Patient as a random effect (multiple measurements per patient)
- Visit (temporal chronological variable)

Secondary Objective G: Initial formulation: Correlate the variation in clinical and imaging parameters with the initial level and changes in the levels of 25(OH)D2 and 25(OH)D3 under treatment.

Reformulated Objective G1: Study the link between the severity of impairment (parameters measured by the baseline MRI, such as the number of lesions, EDSS score) and the vitamin D level measured during pre-screening (25(OH)D2 and 25(OH)D3).

A mixed-effects regression model will be estimated. The model variables will include: - Severity of impairment at inclusion (outcome variable). Several variables will be successively modeled: binary variables for MRI parameters (using a logistic regression model) and a quantitative variable for the EDSS score.

- Levels of 25(OH)D2 and 25(OH)D3 at pre-inclusion (explanatory variables of interest)
- Treatment arm (adjustment variable)
- Center as a random effect (multiple patients per center)

Reformulated Objective G2: Study the link between the occurence of EDA and vitamin D levels (25(OH)D2 and 25(OH)D3) during follow-up.

A mixed-effects regression model will be estimated. The model variables will include:

- Occurrence of EDA (relapse or MRI) (outcome variable)
- Treatment arm (adjustment variable)
- Center as a random effect (multiple patients per center)

- Patient as a random effect (multiple measurements per patient)

- Levels of 25(OH)D2 and 25(OH)D3 measured during follow-up (explanatory variables of interest)

- Visit (temporal chronological variable)

Objectives H, I, and J do not require statistical analyses and involve the establishment of biobanks.

Secondary Objective K: Estimate the discordance rate between the presence of NEL on follow-up MRI scans determined by the neurologist during the study and the result of the centralized MRI analysis performed at the end of the study (EDA not confirmed retrospectively or, conversely, detection of EDA not identified during the study). Additionally, estimate the rate of patients retrospectively identified as erroneously included based on centralized MRI reevaluation (inclusion criterion MRI not verified during centralized reading of the baseline MRI).

Discordance between decisions made during the study by neurologists and the results of centralized reevaluation analyses will be determined for each patient throughout his followup. The discordance rate will be estimated and presented with a 95% confidence interval.

The rate of patients retrospectively identified as erroneously included will also be estimated and presented with a 95% confidence interval.

Anticipated Level of Significance:

A difference will be considered statistically significant when the significance level of the test is less than or equal to 0.05.

Method for Handling Missing, Unused, or Invalid Data:

For the analysis of the primary outcome, if a patient is lost to follow-up without experiencing EDA, they will be considered as NEDA at the end of the 2-year follow-up and censored at the date of the last known status.

Regarding the adjustment variables in the primary analysis:

- If the gadolinium-enhancement status at the diagnostic MRI scan is unknown for a given patient, the missing data will be imputed by the gadolinium-enhancement status at the

baseline MRI scan for that patient if known. If the latter is also missing, the gadoliniumenhancement status used as the randomization stratification variable will be employed.

- When the date of the CIS is missing, it will be extrapolated from the date of the diagnostic MRI scan plus the median time between the CIS and the diagnostic MRI scan.

If the number of T2/FLAIR lesions (used as an indicator of lesion burden, in two categories "<9 lesions " and " >= 9 lesions ") at the baseline MRI is missing, it will be analyzed in a third category "Number of Lesions Missing".

- If the EDSS score is missing at baseline, it will be imputed by the first non-missing EDSS scores at the M3 and M12 visits, subtracting the median of the EDSS score difference between M0 and M3 (respectively between M0 and M12) obtained from patients with scores recorded at both visits. If the result is negative, the median will not be subtracted.

For other secondary outcome measures, no method for imputing missing data is planned.

Analysis population:

Patients who did not receive the study treatment will not be considered in the analyses, which will be conducted on a modified intention-to-treat basis.

All patients who received at least one dose of the study treatment will be included in the analyses.

Thus, the following individuals will not be considered in the analyses:

- Patients with "Study discontinuation at the investigator's decision due to disease activity identified on the baseline MRI" or occurrence of a relapse before treatment onset.

- Patients who withdrew their consent.

- Patients who did not undergo a baseline MRI (withdrawal of consent, inability to undergo MRI).

- Patients lost to follow-up immediately after inclusion (at the inclusion visit and/or baseline MRI), with no follow-up data.

- Patients mistakenly included without MS or with occurrence of a relapse before the baseline MRI.

These patients cannot be included in an intention-to-treat analysis because they have no follow-up and, therefore, no information on disease activity during follow-up.

Bibliographic References

Edgar et al 2021 : Including random centre effects in design, analysis and presentation of multi-centre trials. Trials. 2021, 22:357.

Kahan 2014 : Accounting for centre-effects in multicentre trials with a binary outcome – when, why, and how? BMC Medical Research Methodology, 2014, 14:20.

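### The primary comparison of EDA rates counts patients lost before EDA as disease-free at 2 years, which understates the rates and biases the odds ratio if loss differs between arms

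*SAP*

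**What the plan says.** In Primary Analysis (Rate of EDA), the event is EDA within two years, found by relapse or on MRI at 3, 12 and 24 months. For patients who leave early the rule is: "Patients lost to follow-up before experiencing EDA will be considered as not having had the event". That status feeds both the reported rates and the test: "The rate of EDA in both arms will be estimated and then compared between the two treatment arms using mixed-effects logistic regression". One sensitivity analysis is planned, the maximum-bias analysis. It recodes lost interventional patients as EDA and leaves lost control patients as NEDA.

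Primary Analysis (Time to EDA) treats the same patients differently: "Patients lost to follow-up or not showing EDA during the follow-up will be right-censored at the date of the last news". It produces an adjusted hazard ratio from a random-effects Cox model, and curves: "Time to EDA in both arms will be graphically represented using the Kaplan-Meier method". It plans no comparison of 24-month risks.

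The section on missing data restates both rules together: such patients are handled so that "they will be considered as NEDA at the end of the 2-year follow-up and censored at the date of the last known status". This is not a contradiction, because the first half serves the rate and the second half serves the time to event.

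The Analysis population section bounds who is affected: "All patients who received at least one dose of the study treatment will be included in the analyses". The rule therefore reaches treated patients who leave before EDA.

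**The concern.** NEDA at 24 months is a status established by observation, chiefly by MRI. Here it is assigned because observation stopped. That is correct only if no leaver would have had EDA later. If some would have, the rate is too low in every arm with losses.

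The comparison suffers when the arms lose different numbers of patients, or lose them at different times. The arm that loses more, or earlier, generally looks better. The logistic result can then show an advantage that does not exist or hide one that does, and the two analyses headed primary will disagree more often.

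The maximum-bias analysis moves only the interventional arm. It protects against a false benefit, but it cannot reveal a benefit masked by heavier placebo loss.

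**Working it through.** **Inputs.** The SAP gives the event, the MRI times, the rule, a significance level of 0.05 and a count of 316 patients. It gives no EDA rate, drop-out rate or power, so there is no plan figure to reproduce. Assumed: 158 per arm; a two-sided test; true 2-year risk p of 50, 65 or 80%; a share L of an arm with a drop-out time uniform over 24 months and unrelated to prognosis; 30% of patients with EDA detected at relapse and 70% at the next MRI. Pattern A has a constant hazard. Pattern B has half of EDA by month 3.

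**Step 1: understatement of the rate.** Let D be the probability that EDA was detected before the drop-out time. The rate under the rule is

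p − L(p − D).

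For pattern A, h = −ln(1−p)/24 and F(t) = 1 − exp(−ht). At p = 0.65, 24h = 1.0498.

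- Detected at relapse: mean of F = 1 − 0.65/1.0498 = 0.381.
- Detected at MRI: (3/24)×0 + (9/24)×F(3) + (12/24)×F(12) = 0.375×0.123 + 0.5×0.408 = 0.250.
- D = 0.3×0.381 + 0.7×0.250 = 0.289, so p − D = 0.361.

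Drop-out of 5/10/15% therefore lowers the rate by 1.8/3.6/5.4 points. Pattern B gives 1.3/2.5/3.8 points.

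**Step 2: no true effect.** With unequal amounts of loss, the spurious difference is (difference in L)×(p − D). For 15% v 5% at p = 0.65 this is 0.10×0.361 = 3.6 points. Simulated results (12,000 trials per scenario, unadjusted Wald test of the log odds ratio; triplets are for risk 50/65/80%):

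| Drop-out | Spurious difference, points | Type I error, % |
|---|---|---|
| Equal, 5–15% | none | 4.4–5.2 |
| 6% v 4% | 0.4–0.8 | 4.9–5.4 |
| 12% v 8% | 0.8–1.6 | 5.1–6.0 |
| 10% v 5% | 1.0–2.0 | 5.1–7.1 |
| 15% v 5%, A | 3.0/3.6/4.1 | 8.3/9.7/13.5 |
| 15% v 5%, B | 2.0/2.6/3.0 | 6.4/7.6/9.6 |
| Equal 10%, vitamin D in months 0–12 and placebo in months 12–24, A | 2.4/3.2/4.1 | 7.0/8.8/12.8 |
| The same, B | 1.9/2.4/3.1 | 5.9/7.1/9.9 |

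A simpler calculation on the odds-ratio scale puts all loss at month 6, with a true risk of 60% in both arms. The chance of EDA by month 6 is 1 − 0.4^0.25 = 0.205. Control, 5% lost: 0.95×0.6 + 0.05×0.205 = 0.580. Treated, 15% lost: 0.85×0.6 + 0.15×0.205 = 0.541. The odds ratio is 0.85 where the truth is 1.

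**Step 3: true benefit of 15 points (50% v 65%).** At p = 0.50 the same formula gives p − D = 0.292. With placebo losing 15% and vitamin D 5%, pattern A:

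- Placebo: 65 − 15×0.361 = 59.6%.
- Vitamin D: 50 − 5×0.292 = 48.5%.
- Observed benefit: about 11 points (pattern B: 12.2).

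Power under A/B, against 77% for the logistic test with no drop-out:

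| Analysis | Power, % |
|---|---|
| Logistic, lost counted as NEDA | 50/58 |
| Censored log-rank | 76/75 |
| Kaplan-Meier 24-month risk difference | 75/75 |
| Maximum bias | 23/34 |

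In 27/15% of these trials the censored analysis finds the benefit and the logistic analysis does not. With no drop-out this happens in 4/3%. Equal drop-out of 5/10/15% causes only slight dilution: power is 75/72/69% (A).

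**Step 4: maximum bias.** With no effect it gives a false benefit in 0.7% of trials or fewer. With the true 15-point benefit and equal drop-out of 3/5/10/15%, it confirms the benefit in 60/48/21/5% of trials (A). It is a bound, not an estimate.

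**Step 5: does imputation repair it?** This used 1,400 trials per scenario and 10 imputations, with covariate adjustment but no centre term in imputation or analysis, although the data had centre effects.

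- No effect, 15% v 5%, risk 50/65/80%: imputation deviated from complete data by 0.1 point or less, with type I error 4.6/5.2/4.8%. The SAP's rule deviated by 3.1/3.6/3.8 points, with 9.9/10.9/12.1%. Unadjusted Kaplan-Meier deviated by 0.3 point, with 5.1–6.0%.
- True benefit, placebo losing more: imputation gave 15.1 points and 78% power; the SAP's rule gave 11.2 points and 53%; complete data gave 81% power.

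**The case against.** The strongest objection is that the harm depends on an input nobody has documented. Equal loss leaves the type I error at about 5%, and modest imbalance does little. The larger figures need threefold unequal loss or complete separation in time, and nothing in the SAP points to either. This stands, and it limits the weight of the point.

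Second, both directions of error already have a safeguard: maximum bias against a false benefit, and the censored Cox analysis against a hidden one. In Step 3 the censored log-rank has as much power as the Kaplan-Meier risk difference. That is right as far as the test goes. But the primary objective is the risk within two years. The Cox model corrects neither the reported 24-month rates nor their comparison, and the SAP does not say what to conclude if its two primary analyses disagree.

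Third, the remedy also rests on an untestable assumption. This is true. With 15% v 5% loss and leavers' EDA hazard at 0.25 times the others', the SAP's rule is less biased (1.0–2.0 points, against 2.3–3.4 for Kaplan-Meier). At 0.5 times it is as biased or more so (1.8–3.2 against 1.3–1.7), and at 1.5 times clearly worse (3.6–4.1 against 0.6–0.9). The two are about equal near 0.4. The present rule therefore deserves a place as a sensitivity analysis.

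**Conclusion.** The concern holds. The rule understates the 2-year EDA rate in any arm where leavers would later have had EDA, by about 1.3 to 5.4 points at a 65% risk and 5–15% drop-out. The odds ratio is also biased if loss differs between arms in amount or timing. With no effect and 15% v 5% loss, the type I error rises to 6.4–13.5%. With heavier placebo loss under a true 15-point benefit, power falls from 77% to 50–58%.

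With balanced or mildly unequal loss the test is little affected and only the stated rates are wrong. All sizes assume 158 per arm, the stated risks and detection pattern, and, unless stated otherwise, loss unrelated to prognosis. The actual loss by arm is not in the SAP, so the size in this trial is unknown. It is a defect worth correcting because the correction is cheap; it does not invalidate the design.

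**What to change.** Name one method in advance for the EDA rates and their comparison.

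1. **Multiple imputation.** This keeps the planned adjusted mixed logistic model. Impute under MAR the 24-month status of patients lost before EDA, from arm, the stratification factor, baseline covariates, and the times of last contact and last MRI. Combine by Rubin's rules. State how centre enters the imputation.
2. **Censored 24-month risk.** Estimate the risk by arm and its difference, with 95% CI, from the time-to-EDA data. Use a nominal-visit scale, because the clock starts at first dose but follow-up closes otherwise: "The endpoint date will be established for each patient at the date of the end-of-study visit conducted 24 months (2 years) after inclusion". On the first-dose scale the M24 visit falls at different times for different patients. A plain Kaplan-Meier difference also drops the covariates and the centre effect, which favours option 1.

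Keep both the lost-as-NEDA rule and maximum bias as sensitivity analyses. Report the number and timing of losses before EDA by arm. Align the missing-data section, for example: *for the rate, the 24-month status is obtained by [method chosen]; for time to EDA, the patient is censored when last known to be event-free.*

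The cost is SAP wording and a little programming, with no new data. In the simulations, imputation gave a standard error of the log odds ratio 5–12% above the present rule and 4% above complete data. The result relies on MAR or non-informative censoring, which should be stated.

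### The maximum-bias analysis defines missing data by discontinuation of follow-up, but 2-year NEDA also needs the Month 24 MRI, so the analysis is not a true worst-case bound

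*SAP*

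**What the plan says.** The SAP section Primary Analysis (Rate of EDA) defines the event over the two years of follow-up as "relapse and/or appearance of new or enlarging lesions (NEL) on follow-up MRIs at 3, 12, and 24 months". The same section sets the main handling of losses: "Patients lost to follow-up before experiencing EDA will be considered as not having had the event". It then plans a maximum-bias sensitivity analysis by "considering missing data (discontinuation of follow-up before the end of the 2-year follow-up with NEDA) in the interventional arm as failures", with control-arm missing data counted as successes.

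The section Method for Handling Missing, Unused, or Invalid Data repeats the main rule for this endpoint: "if a patient is lost to follow-up without experiencing EDA, they will be considered as NEDA at the end of the 2-year follow-up". Its remaining imputation rules concern adjustment variables.

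In Primary Analysis (Time to EDA), follow-up closes by visit and contact: "The endpoint date will be established for each patient at the date of the end-of-study visit conducted 24 months (2 years) after inclusion", and "Patients lost to follow-up or not showing EDA during the follow-up will be right-censored at the date of the last news".

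No section says how to classify a patient who reaches 2 years without a recorded relapse or lesion event but has no Month 24 MRI, or has one that cannot be read.

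**The concern.** A worst-case analysis is useful only if every unverified outcome is set to its unfavourable value. Here the endpoint has two parts, relapse and MRI, while missingness is defined by whether the patient left follow-up. The two need not coincide: a patient can complete the 24-month visit without a usable scan. The MRI part of the endpoint is then unknown for the last 12 months, or for 21 months if the Month 12 scan was also missed (24 − 3).

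At stake is the statement that a favourable result withstands the maximum bias. If unscanned vitamin D patients stay successes in that analysis, the statement covers less than it appears to.

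**Working it through.** **1. Setting the rules side by side.** Take a vitamin D patient who attends at 24 months, has had no relapse, had no new lesions on the Month 3 and Month 12 scans, and has no Month 24 MRI.
- Event rule: no relapse and no lesion event recorded, so no EDA.
- Loss rule: not lost to follow-up, so it does not apply.
- Maximum-bias rule: has not discontinued before 2 years, so on the plain wording is not missing and stays a success.
- Time-to-EDA rule: censored at last news, so event-free to about 24 months.

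A missed Month 3 or Month 12 scan alone matters less for the 2-year rate, because a later scan can still show new T2 lesions. The gap concerns the Month 24 scan.

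**2. Effect per patient.** The SAP mentions 316 patients and gives no split by arm. Assuming 316 / 2 = 158 per arm, each unscanned NEDA patient in the vitamin D arm lowers the reported worst-case EDA rate by 1/158 = 0.63 percentage points. For 3, 8 or 16 such patients (2%, 5%, 10%) the understatement is 3/158 = 1.9, 8/158 = 5.1 or 16/158 = 10.1 points.

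**3. Illustration for a favourable result.** The SAP gives no EDA rate, discontinuation rate or missing-scan rate, so there is no stated figure to reproduce and all counts below are assumptions. The test is an unadjusted two-sided comparison of proportions (Pearson chi-square without correction), not the planned mixed logistic model:

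z = (p2 − p1) / √[p(1 − p) × 2/158], with p the pooled rate.

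Scenario A: 87/158 EDA on vitamin D, 117/158 on placebo, 5 vitamin D discontinuations.

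| Unscanned vitamin D patients counted as EDA | Vitamin D | Placebo | p |
|---|---|---|---|
| 0 (as worded) | 92/158 = 58.2% | 74.1% | 0.003 |
| 8 | 100/158 = 63.3% | 74.1% | 0.039 |
| 16 | 108/158 = 68.4% | 74.1% | 0.26 |

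For the middle row: p = 217/316 = 0.687, standard error = 0.0522, difference = 17/158 = 0.1076, z = 2.06.

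Scenario B: placebo/vitamin D rates of 75%/60%, 70%/55% or 60%/45%, with 8 vitamin D discontinuations. As worded, the differences are 9.5 to 10.1 points (p = 0.059 to 0.070). With 3, 8 or 16 unscanned patients also counted as EDA, they fall to 7.6 to 8.2, 4.4 to 5.1 and −0.6 to 0 points. The analysis as worded is already above 0.05 in these cases, so the extra patients change the estimate and not the significance call.

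**4. Direction of the analysis.** Lost control patients are already NEDA in the main analysis, so the maximum-bias analysis moves only the vitamin D arm. In an assumed near-null case (107 vs 110 events, p = 0.72) with 8 missing per arm, the planned direction gives 115/158 = 72.8% vs 110/158 = 69.6% (p = 0.53). The mirrored direction gives 107/158 = 67.7% vs 118/158 = 74.7% (p = 0.17). The sign changes, but neither extreme is significant.

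**The case against.** The strongest reply is that the SAP never says that a patient without a Month 24 MRI is NEDA. It describes the two-year follow-up through its scheduled scans, so a missing Month 24 scan could be read as incomplete follow-up, which would already place the patient in the worst-case set. That reading is open. It is not stated, though, and the other passages tie the end of follow-up to the visit and to last news. A final SAP should not leave the choice to the analyst.

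It is also fair that the number affected is not given and could be zero, and that every rate above is assumed. In scenario A, 8 extra patients leave the result significant; only the 16-patient row loses it. The illustrations do not show that any conclusion of this trial would change.

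Three stronger readings are tempting and not supported:
- A reader might infer that only formal withdrawal counts as missing. Discontinuation of follow-up also covers patients who are lost.
- A reader might infer that a null result would have no missing-data check at all. The Cox analysis censors losses at last news in both arms, which is a second treatment of losses. It does not, however, resolve a missing Month 24 scan in a patient still in contact.
- A reader might infer that moving only one arm is an error. A one-sided worst case against the experimental arm is an accepted check on a positive claim, and the SAP states it openly.

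**Conclusion.** The point holds as a mismatch between the endpoint and the definition of missing data in one sensitivity analysis. On the plain wording, the analysis is not the maximum-bias bound that it is described as, and the rest of the SAP does not close the gap. The understatement is about 0.63 points of the vitamin D EDA rate per affected patient, assuming an equal split of 316. The total effect is unknown because the SAP does not give the number of patients without an evaluable Month 24 scan. The main analysis rule for losses is not in question here, and the one-sided direction of the sensitivity analysis is a limitation of scope and not a mistake.

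**What to change.** In Primary Analysis (Rate of EDA), define missing for the maximum-bias analysis as: no EDA and no evaluable Month 24 MRI, for any reason (withdrawal, loss to follow-up, or visit without MRI). Report the number of such patients per arm.

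Optionally, add the mirrored extreme (missing vitamin D as NEDA, missing placebo as EDA) or a tipping-point table between the two extremes, so that a null or unfavourable result is also bounded.

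The cost is one sentence in the SAP, a count by arm and a rerun of the same model; the optional part adds a few more runs. The small downside is a less favourable worst-case figure.
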